5.2. Study Duration

Study participation will last approximately 8 months, consisting of a minimum of 7 days but no more than 4 week screening phase and baseline visit, and a total of 9 treatment/safety visits over 6 months. If study visit window exceeds 28 days, study drug will be resupplied which may require additional study drug pickup visits. Patients who discontinue treatment will continue follow-up measures as possible and will be analyzed as randomized per the intent to treat principal.

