7.2. Early Withdrawal

If subject withdraws from the study after the screening visit, but before visit 3, no further evaluations are necessary. If subject withdraws from the study after visit 3, all safety assessments will be performed (see section 7.3).

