9. CONCOMITANT MEDICATIONS AND NON-DRUG THERAPIES

9.1. Permitted Medications

Any medication not listed in list of Prohibited/Conditional Medications will be permitted during this study. A record will be kept by site staff detailing doses and indication of any concomitant medications used by subjects.

Table 2: Prohibited Medications

Anticholinergics
Antihistamines (centrally-acting)
Barbiturates
Benzodiazepines
Insulin
Muscle relaxants
Neuroleptics
Opiates

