9.2. Prohibited Medications

Subjects taking prohibited medications at time of screening will not be allowed to participate in study, unless such treatment is discontinued within 30 days. These medications include anticholinergics, and centrally acting antihistamines (e.g. Benadryl), opiates, benzodiazepines, barbiturates, neuroleptics, muscle relaxants, and insulin. For randomized subjects who take a prohibited med (episodic or PRN) will be considered for study continuation on an individual basis. Randomized subjects who take a prohibited med (long-term or for >7 days per concomitant illness/episode) will be withdrawn from study. Randomized subjects needing to initiate a conditional medication or alter dose of conditional medication during study will be considered on an individual basis.

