10.2. Subject Withdrawal

Subject may withdraw from study at any time for any reason without penalty or be terminated from the study by the clinical investigator (see provisions for termination by study team.) Investigational team will document the reason(s) for withdrawal. In the event a subject chooses to withdraw from study before Visit 11, the safety procedures described in Section 7.3 will be performed ideally within 3 days following subject's decision to withdraw. For all subjects who withdraw, all final safety assessments will be collected regardless of time elapsed since previous visit. In addition to the termination visit, subjects who withdraw early will be contacted within 7 days by study staff via telephone to assess development of new and/or ongoing AEs and concomitant medications. All subjects randomized to the study will be included in the analysis as part of their assigned study group regardless of treatment completion, as is consistent with the intent-to-treat principle. .

Subject's participation may be terminated at the discretion of the investigator. Individuals may be withdrawn for the following reasons:

- Clinically significant adverse events.
- Lost to follow-up.
- Protocol violations.
- Inability to tolerate study medication.

- Other.

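### Section 9.2 takes long-term or >7-day users of a prohibited medication out of the study, and no ADAS-Cog 13, CDR or FAQ is scheduled at or after withdrawal, so primary outcomes that could be collected are given up

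*Combined protocol and SAP*

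**What the plan says.** **Withdrawal rule.** Section 9.2 is mandatory for sustained use: "Randomized subjects who take a prohibited med (long-term or for >7 days per concomitant illness/episode) will be withdrawn from study". Discretion exists only for shorter use, "For randomized subjects who take a prohibited med (episodic or PRN) will be considered for study continuation on an individual basis", and for conditional medications. The prohibited list in 9.1 and 9.2 covers anticholinergics, centrally acting antihistamines, barbiturates, benzodiazepines, insulin, muscle relaxants, neuroleptics and opiates.

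**What follows withdrawal.** Section 7.2 asks for the safety assessments of 7.3 if a subject leaves after Visit 3. Section 10.2 says "For all subjects who withdraw, all final safety assessments will be collected regardless of time elapsed since previous visit" and adds a telephone call within 7 days about adverse events and concomitant medications. In the neuropsychological Table 2 (section 7.4), the Early Withdrawal column is marked for GDS and C-SSRS only. ADAS-Cog 13, CDR and FAQ are marked at Visits 2, 7 and 10 and nowhere else.

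**Follow-up and analysis.** Section 5.2 says "Patients who discontinue treatment will continue follow-up measures as possible and will be analyzed as randomized per the intent to treat principal". Section 10.2 says "All subjects randomized to the study will be included in the analysis as part of their assigned study group regardless of treatment completion". Section 12.1 applies intent-to-treat to all randomised subjects whatever their compliance or missing data. It expects little missing data, uses linear mixed models under missing at random, and plans pattern-mixture, multiple-imputation and per-protocol sensitivity analyses. Section 12.2 takes change from baseline to week 12 and to week 24 as the primary outcome variables.

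**The concern.** A rule about concomitant medication is also acting as a rule about outcome collection. A subject who starts an opiate after an injury, or a neuroleptic for behavioural symptoms, may be willing and able to attend Visits 7 and 10. As written, the plan does not measure that subject's primary outcomes there.

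This matters because the reason for removal may be related to the outcome. Starting a neuroleptic, benzodiazepine or opiate can reflect the subject's clinical course, so missing at random is doubtful for exactly these subjects. At stake is how far the primary comparison represents everyone randomised, in a trial of 45 per arm. Values not collected at weeks 12 and 24 cannot be obtained later.

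**Working it through.** No figure in the plan measures this point, so the check is to trace a removed subject through the text.

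1. **Does 9.2 leave room to stay in follow-up?** Not for long-term or >7-day use. Subjects are withdrawn from the study, and the individual consideration in the same section does not extend to this group.

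2. **Is a primary outcome collected at or after withdrawal?** The places that could provide for it are:
   - 7.2: safety assessments only.
   - 10.2: the 7.3 safety procedures, final safety assessments and one telephone call on adverse events and concomitant medications.
   - Neuropsychological Table 2, Early Withdrawal column: GDS and C-SSRS marked; ADAS-Cog 13, CDR and FAQ blank.

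   None schedules a primary outcome.

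3. **What does the primary model receive?** Under 12.2 the responses are change to week 12 (Visit 7) and change to week 24 (Visit 10), with the baseline score as a covariate.
   - Removed before Visit 7: no response on any of the three measures, so no record in the model.
   - Removed between Visits 7 and 10: the week 12 change only.
   - Removed after Visit 10: nothing lost.

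4. **How does that compare with the stated intentions?**
   - 5.2 intends follow-up, as far as possible, after treatment is discontinued. For these subjects 9.2 ends participation instead.
   - 10.2 and 12.1 say all randomised subjects are in the analysis. For removal between Visits 7 and 10, a mixed model on the available data partly honours this. For removal before Visit 7, the primary model cannot honour it.

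5. **Do the planned analyses repair it?** The mixed model uses whatever was observed. Multiple imputation can bring in subjects without a response, and pattern-mixture models can vary the missing-data assumption. All of them stand on assumptions that the uncollected values would have been needed to check.

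6. **How large is it?** The documents give no rate of prohibited-medication use and no withdrawal rate, so neither the number affected nor a bias can be computed.

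**The case against.** **The sections need not conflict.** Section 5.2 concerns patients who discontinue treatment, and only as far as possible; 9.2 concerns subjects withdrawn from the study. These can be separate categories, and 10.2 and 12.1 describe analysis, not data collection. A reader might infer a flat contradiction, and the documents do not support that. What stands is that 9.2 puts these subjects in the category without outcome follow-up. The boundary is also unclear, because 10.2 lists inability to tolerate study medication among the reasons for withdrawal.

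**Not testing cognition under these drugs is a recognisable choice.** Exclusion 6 restricts medications partly because of cognitive testing. This is fair, and it is a reason to report such values separately. It is a weaker reason not to collect them when 12.1 already plans a per-protocol analysis.

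**The group may be small.** Current users are screened out unless they stop, and episodic or PRN use is judged individually. This stands.

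**A reader might infer a loss of power that retention would restore.** The documents do not support that. Using the two-sided two-sample t-test at 0.05 with the 12.4 inputs for FAQ (difference 2, SD 3.6, 45 per arm), the noncentrality is 2 / (3.6 × √(2/45)) = 2.635 and power is 74.1%, as printed. The loss shares below are assumptions and are not tied to 9.2. If those subjects are retained with no remaining treatment difference, the overall difference shrinks in proportion, for example 2 × 81/90 = 1.8 at 10%:

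| Assumed share | Lost (numbers left) | Retained, no effect left | Retained, half the effect left |
|---|---|---|---|
| about 5% | 72.1% (43 v 43) | 70.2% | 72.2% |
| 10% | 69.5% (41 v 40) | 65.0% | 69.7% |
| about 15% | 66.6% (38 v 38) | 59.5% | 67.1% |

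Retention gains power only if stoppers keep more than about half the effect. The case therefore rests on bias and on who is represented.

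**A reader might also infer damage to the secondary objective in diabetes**, since insulin is prohibited. That objective concerns non-insulin dependent diabetes. A subject moved to long-term insulin no longer fits it, and final safety assessments are still collected.

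**Conclusion.** The point holds as a cheap improvement. As written, 9.2 creates avoidable and possibly informative missing primary outcomes: all of them for a subject removed before Visit 7, and week 24 for one removed between Visits 7 and 10. This works against the intent of 5.2 and the inclusion statements of 10.2 and 12.1; the last two are flatly unmet in the primary model only for removals before Visit 7.

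The reading of the text is secure. The consequence is not quantified: frequency, size and direction of bias are all unknown. That the missingness may be informative is a judgement about why such drugs are started, and the documents do not show it. A reader might infer that the trial result would be biased in a particular direction; nothing in the plan supports that.

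**What to change.** - **9.2:** for long-term or >7-day use, replace 'withdrawn from study' with 'discontinued from study drug'.
- **5.2, 7.2 and 10.2:** state that such subjects who still consent, and for whom the investigator judges it safe, are assessed with ADAS-Cog 13, CDR and FAQ at the scheduled Visits 7 and 10. The existing provision, "Subject's participation may be terminated at the discretion of the investigator", can stay.
- **12.1:** state that these values enter the intent-to-treat analysis, and that outcomes measured after prohibited-medication use are excluded from the per-protocol sensitivity analysis. Keep the pattern-mixture and multiple-imputation analyses for outcomes that are still missing.

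**Cost.** Wording in five sections and the assessments themselves for the subjects retained. No new visit type is needed, because Visits 7 and 10 already include these tests. The downside is that some intent-to-treat outcomes will be measured off study drug or on a cognition-active medication, which may dilute the estimated effect. Section 5.2 already accepts follow-up after treatment stops, and the per-protocol rule shows the result without those values.

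No change to the medication record is requested. Section 9.1 says "A record will be kept by site staff detailing doses and indication of any concomitant medications used by subjects" and does not mention dates, but the case report forms are not among the documents, so it cannot be shown that dates are missing.

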10. SUBJECT COMPLETION AND WITHDRAWAL

10.1. Subject Completion

Subjects completing all 11 study visits will be considered to have completed study.

10.2. Subject Withdrawal

Subject may withdraw from study at any time for any reason without penalty or be terminated from the study by the clinical investigator (see provisions for termination by study team.) Investigational team will document the reason(s) for withdrawal. In the event a subject chooses to withdraw from study before Visit 11, the safety procedures described in Section 7.3 will be performed ideally within 3 days following subject's decision to withdraw. For all subjects who withdraw, all final safety assessments will be collected regardless of time elapsed since previous visit. In addition to the termination visit, subjects who withdraw early will be contacted within 7 days by study staff via telephone to assess development of new and/or ongoing AEs and concomitant medications. All subjects randomized to the study will be included in the analysis as part of their assigned study group regardless of treatment completion, as is consistent with the intent-to-treat principle. .

Subject's participation may be terminated at the discretion of the investigator. Individuals may be withdrawn for the following reasons:

- Clinically significant adverse events.
- Lost to follow-up.
- Protocol violations.
- Inability to tolerate study medication.

- Other.

11. ADVERSE EVENTS (AE) AND SERIOUS ADVERSE EVENTS (SAE)

11.1. Definition of AE

An adverse event is any symptom, sign, illness or experience which develops or worsens in severity during the course of the study. Intercurrent illnesses or injuries should be regarded as adverse events. Abnormal results of diagnostic procedures are considered to be adverse events if the abnormality:

- Results in study withdrawal.
- Is associated with clinical signs or symptoms.
- Leads to treatment or to further diagnostic tests.
- Is considered by the investigator to be of clinical significance.

11.2. Definition of SAE

Adverse events are classified as either serious or non-serious. A serious adverse event is any event that results in:

- Death.
- Life-threatening situation.
- Hospitalization or prolongation of hospitalization.
- Disability or incapacitation.
- Other events determined by investigator to be medically significant in which subject's well-being is jeopardized (e.g. events that have high likelihood of escalating to the point of meeting criteria outlined above)

11.2.1. Clinical Laboratory Abnormalities & Other Abnormal Assessments as AEs & SAEs

Any new abnormal, vital, examination, or laboratory finding judged clinically significant by the investigator will be documented as an AE or SAE, if meeting the definitions for such. Abnormal lab findings or other abnormal assessments associated with the disease under study will not be considered AEs or SAEs unless more severe than expected, as judged by the investigator.

11.2.2. Time Period and Frequency of Detecting AEs and SAEs

Upon consenting, a subject is considered to be a participant in the study, and until that person either withdraws or completes study, AEs and SAEs will be recorded. The investigational team will promptly report any AE/SAE as required per federal guidelines.

12. DATA ANALYSIS AND STATISTICAL CONSIDERATIONS

12.1. Analysis Overview

Measures of central tendency and spread will be computed for the study population and by treatment group for each outcome variable. These summaries will describe patient characteristics, confirm that randomization produced a balanced design, and confirm that the planned analyses are appropriate for the distribution of the outcome variables.

Missing data are expected to be minimal. Therefore, the primary analyses will follow an intent-to-treat principal and include all randomized subjects regardless of intervention compliance and missing data. We will use linear mixed models, an analytic approach that can accommodate unbalanced data and use all available observations in the analysis by assuming data are missing at random. Sensitivity analyses will include evaluation of missing assumptions using pattern mixture models and multiple imputation and a per-protocol approach to accommodate subjects who do not adhere to the intervention protocol.

All statistical tests will be conducted in SAS Version 9.4 and will be evaluated using a two-sided 0.05 level of significance.

12.2. Statistical Analysis of Efficacy Outcomes

Previous research has shown that the primary outcomes (ADAS-Cog 13, CDR-SOB, and FAQ) to be highly correlated. Therefore, to increase power and account for this correlation, the primary analysis will be a multivariate, linear mixed-effects regression. Specifically, the change in cognition and function measures between baseline and week 12 and between baseline and week 24 will serve as the primary outcome variables. We will include intervention arm, intervention week, intervention arm*week, age, and baseline test scores as fixed effects. The efficacy of intranasal (IN) insulin on cognition and function will be tested on the intervention arm*week interaction. Age and baseline test scores are included because of the possibility of unequal baseline values. Random intercept effects will be included to account for the nested structure of the data, multiple outcomes and observation points.

First, the assumptions of such a model will be verified. That is, the dependent variables will be tested for: (1) multivariate normality, (2) homoscedasticity, (3) equality of covariance matrices, and (4) independent observations. These outcome variables have been analyzed after log-transformation in previous studies because they have a distribution skewed to the right. We will confirm that this transformation is suitable for our study. If outcome variables are log-transformed, efficacy measures will correspond to percent change of cognitive outcomes.

To protect against type I error, efficacy of IN insulin will be considered if an overall cognitive decline is observed relative to placebo. Efficacy measures for composite cognitive and functional decline with corresponding 95% confidence intervals and p-values will be reported.

For the analysis of secondary cognition and function measures (Digit Span, Trailmaking, COWAT, Animal Naming, and WMS), secondary mood measure (GDS), and exploratory smell measure (AST) we will follow the same approach as for the primary outcomes. We have not included these tests as primary endpoints because they measure more specific effects of AD language, memory, mood, or olfaction impairment and, therefore, may be less sensitive to overall cognitive change in MCI/AD patients. Each outcome measure will be tested in its own linear mixed-effects regression model with measures from baseline to week 12 and baseline to week 24 as the outcome variables. The efficacy of IN

insulin on each measure will be tested on the intervention arm*week interaction. Efficacy measures with corresponding 95% confidence intervals and p-values will be reported.

Exploratory measures of sleep (Sleep Questionnaire and ESS) and biomarkers (CSF Abeta, tau, and phosphotau) will follow the same approach as for the primary outcomes. Two multivariate linear mixed-effects regression models will be fit with change in either sleep or biomarker measures from baseline to visit 7 and baseline to visit 10 as the outcome variables. The efficacy of IN insulin on sleep will be tested on the intervention arm*week interaction. Efficacy measures for composite sleep decline with corresponding 95% confidence intervals and p-values will be reported.

Exploratory PET metabolism will be measured in four cortical ROIs primarily affected by AD: precuneus, posterior cingulate, and bilateral parietotemporal. A multivariate regression model will again be applied to the imaging outcome measures. Specifically, standardized change in posterior cerebral metabolism in the four ROIs from baseline to 6 months will serve as the outcomes. Intervention arm, age, and baseline test scores will be used as fixed effects. Tests of assumptions and interpretation will be similar to that described for primary outcomes. Overall cerebral metabolism and metabolism at each of the four cortical ROIs efficacy measures with corresponding 95% confidence intervals and p-values will be reported.

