6. STUDY POPULATION

6.1. Eligibility Criteria

6.1.1. Inclusion Criteria

A subject will be included for consideration in this study only if all of the following criteria are met:

1. Male or female subject with a clinical and research diagnosis of amnesic-mild cognitive impairment (1, 2) OR probable mild AD in accordance with NINCDS-ADRDA criteria (3).
2. Subject has a MOCA score of 18-27.
3. Subject has a Hachinski Ischemia Score ≤ 4 .
4. Subject is ≥ 50 and <90 years of age.
5. Female subjects must be at least 2 years post-menopausal or surgically sterile.
6. The subject must be proficient in speaking, reading and understanding English in order to comply with procedural testing of cognitive function, memory and physiology.
7. Subject has a dedicated family member/study partner, who will be able to attend all visits and report on subject's status.
8. Subject and family member/study partner have both provided fully informed written consent prior to participation. In the event that subject is legally unable to provide informed written consent due to deterioration in cognitive abilities, fully informed written consent must be provided by a legally authorized representative.
9. If AD, subject must have a brain CT or MRI in initial diagnostic workup or subsequent care that is compatible with the diagnosis of probable Alzheimer's disease.

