8.3. Treatment Assignment

Randomization will be stratified by MOCA score (high = 23-27; low = 18-22), presence of non-insulin dependent diabetes, and APOE4 status *a priori* by the permuted block method. The trial is a double blinded study so that the subject, the investigator, and the trial coordinator will be unaware to which treatment group the subject has been randomized. To facilitate subject blinding, all subjects will undergo the same follow-up procedures. One investigative team member at the site will be unblinded to randomization and prepare the study dose for each subject. This person will not have responsibility for obtaining any study data. An electronic database will be used for automated randomization of participants using a table generated by the statistician.

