12.4. Study Power

A total of n=90 subjects will be randomized to receiving either IN glulisine (n=45) or placebo (n=45) two times daily. The study is powered on the three primary outcomes, ADAS-Cog 13, CDR-SOB, and FAQ.

	Control Group Mean	Standard Deviation	Minimum Detectable Difference	Power
ADAS-Cog 13	19.2	4.6	3	88.426
CDR-SOB	7.9	1.3	1.5	99.972
FAQ	11.56	3.6	2	74.100

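### The efficacy models leave out the three randomisation factors and diagnosis, which can cost precision in the between-arm estimates and leaves chance imbalance on diagnosis only partly adjusted

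*Combined protocol and SAP*

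**What the plan says.** Section 8.3 sets the randomisation: "Randomization will be stratified by MOCA score (high = 23-27; low = 18-22), presence of non-insulin dependent diabetes, and APOE4 status". Section 5 lists the same three factors. Diagnosis is not among them, although section 6.1.1 admits either condition: "Male or female subject with a clinical and research diagnosis of amnesic-mild cognitive impairment (1, 2) OR probable mild AD". The screening visit (section 7.1.1) reviews the research diagnosis, so the variable is available before randomisation.

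For the primary analysis, section 12.2 says: "We will include intervention arm, intervention week, intervention arm*week, age, and baseline test scores as fixed effects". Random intercepts are added and efficacy is tested on the arm-by-week interaction. Age and baseline scores are there to guard against unequal baselines. The secondary, sleep and CSF models follow the same approach. The PET model has a single change score and uses arm, age and baseline scores, so there the arm term itself carries the treatment effect.

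The sensitivity analyses in section 12.1 deal with missing data and adherence. None adds the stratification factors or diagnosis, and no reason is given for leaving them out.

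**The concern.** An analysis normally conditions on the factors used to restrict the randomisation. Stratification removes between-arm variation due to those factors from the estimate. A model that omits them leaves that variation in the residual, so the standard error of a between-arm difference is too large for the design, and any precision the factors could have bought is not collected.

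Diagnosis raises a second issue. The Definitions describe amnesic MCI by preserved instrumental daily living and mild AD by CDR=1, and FAQ and CDR-SOB are two of the three primary outcomes. Diagnosis is thus closely tied to what is measured, is not stratified, and is not modelled. Baseline scores describe where a subject starts. They need not capture how fast the subject declines. The plan's own reason for adjusting for age and baseline scores applies equally here.

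At stake are the width of the confidence intervals for the reported treatment effects and some avoidable chance imbalance.

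**Working it through.** **Inputs from the documents.** Sample size (section 12.4): "A total of n=90 subjects will be randomized to receiving either IN glulisine (n=45) or placebo (n=45) two times daily". Tests (section 12.1) "will be evaluated using a two-sided 0.05 level of significance". Power table rows, in the order control mean, SD, difference, power: "ADAS-Cog 13 19.2 4.6 3 88.426" and "CDR-SOB 7.9 1.3 1.5 99.972"; for FAQ the SD is 3.6, the difference 2 and the power 74.100%.

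**Not in the documents, so assumed.** Extra residual variance explained by the four factors (R²): 0 to 30%. Share of subjects with AD: 30 to 70%.

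**Step 1: reproduce the stated power.** Two-sample t-test with 88 df and noncentrality = difference / (SD × √(2/45)).
- FAQ: 2 / (3.6 × 0.2108) = 2.635, power 74.100%. Matches.
- CDR-SOB: 1.5 / (1.3 × 0.2108) = 5.473, power 99.972%. Matches.
- ADAS-Cog 13: 3 / (4.6 × 0.2108) = 3.094, power 86.426%. The table has 88.426%, which looks like a one-digit slip.

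The plan is therefore powered on an unadjusted between-arm comparison and credits no covariate with any precision.

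**Step 2: between-arm power if the factors are added.** Replace SD by SD × √(1 − R²) and keep 88 df. This treats the tabulated SD as the SD before the factors are added; section 12.4 does not say whether it is a residual SD.

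| Extra R² (assumed) | FAQ | ADAS-Cog 13 | Equivalent N = 90/(1 − R²) |
|---|---|---|---|
| 0 | 74.1% | 86.4% | 90 |
| 5% | 76.2% | 88.1% | 94.7 |
| 10% | 78.5% | 89.7% | 100 |
| 20% | 83.0% | 92.8% | 112.5 |
| 30% | 87.6% | 95.5% | 128.6 |

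CDR-SOB stays at 99.97% or more throughout.

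**Step 3: size of the test if balanced strata are ignored.** If the strata explain a share v of the variance left in the model and are perfectly balanced, the true two-sided level of a between-arm test is 2 × [1 − Φ(1.96/√(1 − v))]. For v = 5%, 10% and 20% this is 0.044, 0.039 and 0.028. The error is on the conservative side.

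**Step 4: chance imbalance on diagnosis.** With half the subjects AD and no stratification on it, the arm difference in AD share has SD √(2 × 0.25/45) = 0.105. The exact (hypergeometric) chance of a difference of at least 10, 15 or 20 percentage points is 40%, 21% and 9%. With 30% or 70% AD it is 36%, 17% and 6.5%. These are upper figures, because they ignore the balancing that MOCA strata bring. If AD subjects changed 2 ADAS-Cog points more over 24 weeks (assumption), the 95% range of the shift at week 24 would be ±1.96 × 0.105 × 2 = ±0.41 points before any adjustment for baseline scores. If that excess built up linearly, 1 point would fall between weeks 12 and 24, and the shift in arm-by-week would be about ±0.2.

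**Step 5: the planned test.** With changes at weeks 12 and 24 as outcomes, arm-by-week compares the arms on the within-subject difference Y24 − Y12. A time-constant covariate entered as a main effect adds the same amount to both terms and cancels. In one simulated complete data set (assumed effects of 1.5 points for diagnosis and 0.7 for APOE4, constant over time), the estimate was −1.4482 and the SE 0.9856 with and without the four factors. With 13 of 90 week-24 values removed, the SE went from 1.078 to 1.074.

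**Step 6: is a gain assured?** No. In the same data set the SE of the week-24 arm difference rose from 0.986 to 1.013 when all four factors were added. In repeated simulated trials under assumed effects, the empirical SD at week 24 fell from 0.843 to 0.828, while for arm-by-week it was essentially unchanged (0.696 against 0.697) even with factor-by-week terms.

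**The case against.** The strongest reply is that the designated efficacy test is arm-by-week, which main effects leave untouched. This stands for complete data, and it means that the figures in step 2 do not describe the planned test. It does not dispose of the point. Section 4.1 defines the ADAS-Cog endpoint as change to each of the two visits, section 12.2 promises efficacy estimates with confidence intervals, the PET model tests arm directly, and the power table itself rests on a between-arm comparison.

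Second, diagnosis is partly covered. Baseline CDR-SOB and FAQ carry much of what separates the two diagnoses, and MOCA band is balanced by design. This also stands, and it is why step 4 gives upper figures. Section 12.2 does not say whether each outcome is adjusted for its own baseline or for all three.

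Third, chance imbalance is random error already reflected in the confidence interval. Under the 2-point assumption its SD is 0.105 × 2 = 0.21, against an unadjusted ADAS-Cog SE of 4.6 × 0.2108 = 0.97, about 5% of the variance. This is correct: it is a precision matter and not a bias.

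A reader might also infer that balance on MOCA band, diabetes and APOE4 is given up. It is not; permuted blocks within strata secure it whether or not the factors are modelled. Nor do the documents show APOE4 to be prognostic. Section 1.1 describes it as a possible modifier of response, which a main effect does not address.

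**Conclusion.** The omission is real and unexplained, and its consequence is modest. For between-arm estimates (weeks 12 and 24, PET), standard errors ignore the stratification and some precision may be forgone. Chance imbalance on diagnosis is only partly adjusted for. If the four factors explained a further 5-10% of residual variance, FAQ power for a between-arm contrast would be about 76-78% instead of 74%. That range is an assumption, and the gain could be near zero.

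Two stronger readings are not supported. One is that the planned analysis is invalid: ignoring balanced strata makes a between-arm test conservative. The other is that adding main effects would raise the power of the arm-by-week test: with complete data it would not.

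**What to change.** Pre-specify MOCA band, non-insulin dependent diabetes, APOE4 status and diagnosis as fixed effects in the primary, secondary and PET models. If arm-by-week remains the efficacy test, add factor-by-week terms, at least diagnosis-by-week. These remove the effect of a diagnosis imbalance on that contrast, though little or no reduction in its standard error should be expected. State also which baseline scores enter for which outcome. If the factors are to stay out, give the reason. Either way, settle it before unblinding so that covariates are not chosen after the results are seen.

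Randomisation can stay as it is. Stratifying on diagnosis too would turn 8 strata averaging 90/8 = 11.25 subjects into 16 averaging 90/16 = 5.6, so adjustment is the more practical remedy.

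The cost is SAP wording and four degrees of freedom per outcome, or up to eight with week terms. In the multivariate model with outcome-specific coefficients this becomes 3 × 4 = 12, or 3 × 8 = 24, parameters. The burden is relatively heavier in the PET substudy, which is a subset whose size the documents do not state.
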